This is a Phase 2, Prospective, Randomized, Multicenter, Open-Label, Controlled Trial. Patients are randomized to treatment with Exenatide SR + SOC vs. SOC alone at 4 months or 12 months post transplant after kidney transplantation and followed until 24 months after kidney transplantation. Patients who discontinued medication for AEs will be contacted within 30 days to follow up on the resolution of symptoms.

Study participants with prediabetes at 4 months or 12 months after kidney transplantation will be randomized 2:1 to receive either Exenatide SR or diet and exercise only with no medication. We plan to enroll approximately 50% of subjects at 4 months post transplant and 50% of subjects at 12 months post transplant

Primary Endpoint is the incidence of diabetes at 24 months after kidney transplantation.

Patients will be followed for 2 years after transplantation (20 or 12 months after enrollment) for progression to all endpoints. Therefore, there will be three SOC biopsies—4, 12 and 24 months after transplantation. Hemoglobin A1C will be performed at the same time points. In addition 2hOGTT will be performed if clinically indicated per our SOC.

Study Sites: This is a multicenter study involving the three Mayo Clinic kidney transplant programs. This group has a common IRB and can contract centrally. Collectively, they perform approximately 600 kidney transplants per year. They have a history of multicenter research trials—they enrolled 480 patients along with a fourth center in a recent NIH-sponsored trial that required a 1 year kidney biopsy (NCT01782586 Validation of Gene Expression Markers of Renal Allograft Functional Decline (<https://clinicaltrials.gov/ct2/show/NCT01782586?term=[name]&rank=10>)). Thus, this consortium is large enough to ensure enrollment in the time frame suggested, yet small enough to ensure collaboration and uniformity needed for these studies.

The patient visits and follow-up including safety laboratories all fall within the SOC follow-up at all sites. These include the biopsies. All clinical standard of care labs and biopsies are followed by clinical operating protocols and are followed by clinical nursing and physician staff.

Study drug:

Exenatide SR

Background.

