(DMGS). 77% of patients with diabetic nephropathy on 10 year biopsy did not have diabetes pre-transplantation, and 46% were in patients without overt diabetes pre- or post-transplantation, but with characteristics of prediabetes including fasting hyperglycemia and obesity. Furthermore, kidney transplants with DMGS had greatly inferior graft survival (Figure 1). These data suggest that a paradigm shift is needed to improve the long-term graft survival for kidney transplants.

PTDM is a pervasive problem. In a review of UTHSA kidney transplant recipients, the incidence of PTDM was 43% among Hispanics and 33% in non-Hispanic whites. Patients with PTDM had a higher BMI (BMI=30.4 kg/m²) compared with patients without PTDM (BMI=27.7 kg/m²). Based on preliminary data from our collaborative analysis of the University of Michigan Transplant Center cohort, 15% of 345 kidney transplant recipients who did not have diabetes pre-transplant had developed PTDM based on an OGTT done at 6 months post-transplant, and another 24% were prediabetic based on 2-hour glucose values which met the criteria for IGT. Similarly, the Mayo experience (a predominantly Caucasian population) noted a 33% incidence of IFG at 1 year among kidney transplant recipients without diabetes pre-transplant.

Study endpoints

Primary Efficacy Endpoint:

Incidence of diabetes at 24 months after kidney transplantation.

Diabetes is defined based on ADA criteria for diagnosis of diabetes;

HbA1C>6.5%

or FPG>126 mg/dl (fasting is defined as no caloric intake for at least 8 hours)

or 2h plasma glucose >200 mg/dl during an OGTT

or random plasma glucose >200 mg/dl in patient with classic symptoms of hyperglycemia

Based on published data, we expect that 30% of untreated patients with prediabetes at 4 months will develop diabetes by 12 months after transplantation. See statistical assessment section.

Patients also will be followed up to 20 months after enrollment for progression to other endpoints

Secondary endpoints

- To evaluate the prevention of progression to diabetes by 24 months after transplantation
- To evaluate the safety and tolerability of Exenatide SR
- To compare hemoglobin A1c levels in patients treated with Exenatide SR + SOC vs. SOC alone at 24 months after kidney transplantation.
- To compare the incidence of mesangial expansion >20% in patients treated with Exenatide SR + SOC vs. SOC alone at 24 months after kidney transplantation.

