Sponsor must also indicate, either in the SAE report or the cover page, the causality of events in relation to all study medications and if the SAE is related to disease progression, as determined by the principal investigator.

PI or co-PI will send SAE report and accompanying cover page by way of email to AstraZeneca's designated mailbox: [REDACTED]

If a non-serious AE becomes serious, this and other relevant follow-up information will be provided to AstraZeneca and the FDA.

Serious adverse events that do not require expedited reporting to the FDA still need to be reported to AstraZeneca preferably using the MedDRA coding language for serious adverse events.

Safety/Tolerability Outcomes Measures:

1. Percentage of Participants with at Least 1 Grade ≥ 2 Treatment Emergent Adverse Event (TEAE) According to Common Terminology Criteria for Adverse Events (CTCAE)

A treatment-emergent adverse event (TEAE) is defined as an adverse event with an onset that occurs after receiving study drug (AE start date greater than or equal to \geq first dose date) and within 30 days after receiving the last dose of study drug (AE start date - last dose date less than or equal to \leq 30). A TEAE may also be a pre-treatment adverse event or a concurrent medical condition diagnosed prior to the date of first dose of study drug, which increases in intensity after the start of dosing.

2. Percentage of Participants with at Least 1 Serious Adverse Event (SAE)

A serious adverse event (SAE) is any untoward medical occurrence or effect that at any dose results in death, is life-threatening, requires inpatient hospitalization or prolongation of existing hospitalization, results in persistent or significant disability / incapacity, is a congenital anomaly / birth defect or is medically important due to other reasons than the above mentioned criteria.

3. Percentage of Participants with at Least 1 Adverse Event Leading to Discontinuation of Investigational Study Medication

Withdrawal due to an AE will occur if the participant experiences an AE that requires early termination because continued participation imposes an unacceptable risk to the participant's health or the participant is unwilling to continue because of the AE.

Safety reporting plan

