Safety will be assessed using incidence of all adverse events (AEs), serious adverse events (SAEs), treatment-emergent adverse events (TEAEs) and AEs leading to study withdrawal; review of laboratory data, including hematology, renal function, biochemistry and microbiology and malignancies; new concomitant medication usage; hospitalization rates; and vital signs. Adverse events will be classified for serious adverse events using standard regulatory criteria.

Statistical analysis plan.

Study design and analysis will be performed according to intention to treat principles. Time to development of PTDM will be compared utilizing Kaplan-Meier curves generated according to the product limit method utilizing log-rank tests to evaluate intergroup differences. Risk adjustment for baseline differences between groups will be assessed according to multivariate proportional hazards models. Data on patients who withdraw or are lost to follow-up will be censored at the time of last visit. Comparisons of repeated measures between groups including the secondary endpoints outlined above will be performed utilizing general linear mixed models with transformation of data to logarithm forms when appropriate. These comparisons will be made with inclusion of subjects who withdraw within the follow-up period. Sensitivity analysis excluding these patients will also be performed.

Needed sample size was calculated according to development of PTDM based on utilization of a 2-sided chi-squared test at a 5% significance level and 80% power. The incidence of PTDM reported after kidney transplant varies from 2-50% with best estimates indicating that approximately 30% of patients will develop PTDM.^{3,4,41,42} The SCALE trial comparing GLP-1 receptor agonists to placebo showed an 80% reduction in development of type 2 diabetes.²¹ Other clinical trials evaluating prevention of diabetes showed a 30% risk reduction with metformin and 55-72% reduction with TZDs.^{29,43} Thus, sample size was calculated based on a proportion of 30% incidence of PTDM in the control group and 80% risk reduction in the experimental group (consistent with SCALE trial). A total of 81 (54:27 according to 2:1 randomization) patients will be required to achieve the power and significance levels above. In our preliminary data, 24-33% of kidney transplant recipients meet prediabetes criteria. We would expect that full enrollment would take 24 months.

Data management plan

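### The grade ≥2 TEAE percentage is defined by dose dates and so has no value in the SOC arm; add a descriptive two-arm grade ≥2 AE and SAE table running from randomisation

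*Combined protocol and SAP*

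**What the plan says.** **The measure.** In *Safety/Tolerability Outcomes Measures*, item 1 is the percentage with at least one CTCAE grade ≥2 TEAE. A TEAE arises in one of two ways. It is "an adverse event with an onset that occurs after receiving study drug", with a start date from the first dose to 30 days after the last. Or it is a pre-existing event or condition "which increases in intensity after the start of dosing". Item 2 is the percentage with at least one SAE, and its definition does not depend on dosing.

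**The arms and follow-up.** Under *Study design/schedule*, patients are "randomized 2:1 to receive either Exenatide SR or diet and exercise only with no medication". Follow-up to 24 months after transplant lasts "20 or 12 months after enrollment", depending on enrolment time, with about half enrolled at each time point.

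**The objective.** It reads "To evaluate the safety and tolerability of Exenatide SR" (*Study objectives*, *Secondary endpoints*).

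**What is already collected.** *Study recording period and follow-up* has AEs and SAEs recorded from consent through the follow-up period, with no limit by arm. Both *Safety reporting plan* sections list the incidence of all AEs and of SAEs. They state no CTCAE cut, common window or layout by arm.

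**Other timing rules.**
- Patients who stop treatment are followed for 30 days for delayed AEs (end of *Stopping Rules*).
- SAE reporting ends 90 days after the last dose (*Study recording period and follow-up*).
- Open-ended AE contacts are timed from the start of drug (*Collecting, monitoring and reporting of serious adverse events*).
- *Schedule of visits* times the first contact from enrolment and does not separate the arms.

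**The concern.** The only graded safety percentage in the plan cannot be calculated for the randomised control. If the rule is applied anyway, SOC scores 0 of 27 by construction, which is not an observed rate.

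This matters because background events are expected. *Standard care* puts mycophenolate in the standard immunosuppression, and the *Rationale* section says it causes gastrointestinal effects similar to those of the study drug and calls the interaction a gap in knowledge. A grade ≥2 percentage from exenatide patients alone mixes drug effect with that background.

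CTCAE grade is specified only for the TEAE measure; elsewhere the investigator simply assesses severity. If SOC events are not graded as they are recorded, a comparable SOC figure may be hard to recover later.

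**Working it through.** **1. Arm sizes.** The plan states no expected grade ≥2 rate, so there is no safety figure to reproduce. The arm sizes used below come from the SAP sample size and do reproduce. Inputs: 30% in SOC, an 80% reduction (so 6% on exenatide), two-sided 5%, 80% power, 2:1 allocation. Pooled rate = (0.30 + 2 × 0.06)/3 = 0.14.

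n(SOC) = [1.96·√(1.5 × 0.14 × 0.86) + 0.8416·√(0.30 × 0.70 + 0.06 × 0.94/2)]² / 0.24² = (0.833 + 0.411)²/0.0576 ≈ 26.9, so 27. With 54 on exenatide the total is 81 (power 80.2%).

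**2. Who has a value.**

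| Rule | Anchor | Exenatide | SOC |
|---|---|---|---|
| TEAE, new onset | first dose to last dose + 30 days | defined | no dose date |
| TEAE, worsening | start of dosing | defined | no dose date |
| SAE percentage | none stated | defined | defined |
| SAE reporting end | last dose + 90 days | defined | no end date |
| AE/SAE recording | consent through follow-up | defined | defined |

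At most 54 of 81 patients have a value for item 1. No section gives SOC a substitute reference date. With a window starting at randomisation, all 81 have one.

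**3. What an exenatide-only figure leaves open.** Assume 22 of 54 exenatide patients have a grade ≥2 event: 40.7%, Wilson 95% CI 28.7 to 54.0%. Item 1 reports this whatever happens in SOC. Newcombe 95% CIs for the difference, exenatide minus SOC:

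| SOC events | SOC % | Difference (points) | 95% CI |
|---|---|---|---|
| 5/27 | 18.5 | +22.2 | 0.4 to 39.1 |
| 6/27 | 22.2 | +18.5 | −3.6 to 36.2 |
| 11/27 | 40.7 | 0.0 | −22.1 to 21.0 |
| 17/27 | 63.0 | −22.2 | −41.9 to 0.7 |
| 18/27 | 66.7 | −25.9 | −44.9 to −2.9 |

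The interval lies above zero for 0 to 5 SOC events, includes zero for 6 to 17, and lies below zero from 18 up.

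**4. Precision of a two-arm table.** With a common rate p, the half-width is 1.96·√[p(1−p)(1/54 + 1/27)] = 1.96·√[p(1−p)/18].
- p = 10%: 1.96·√(0.09/18) = 13.9 points
- p = 30%: 1.96·√(0.21/18) = 21.2 points
- p = 50%: 1.96·√(0.25/18) = 23.1 points

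By exact binomial enumeration in 1-point steps, the true excess needed for at least an 80% chance that the Newcombe interval lies above zero is 28 points at SOC 10%, 33 at 30% and 31 at 50%.

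**5. Exposure.** With a 50:50 enrolment mix, mean planned follow-up is 0.5 × 20 + 0.5 × 12 = 16 months in each arm: 54 × 16 = 864 and 27 × 16 = 432 patient-months.

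**6. Contact timing.** The AE section gives days 7 to 14 and 90 ± 7 after drug start. The schedule gives 7 ± 3 (days 4 to 10) after enrolment, and 90 ± 7. Drug starts at randomisation (*Intervention group*). If enrolment and randomisation fall together, days 7 to 10 satisfy both texts for exenatide. For SOC, the AE section read alone supplies no contact and the schedule supplies two. The 4-month schedule also marks contacts at the three-monthly points from 12 to 24 months; the 12-month schedule does not.

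**The case against.** The objective is to evaluate exenatide, whereas the neighbouring kidney-function, death and graft-loss objectives refer to both arms. Item 3, discontinuation of study medication, also applies only to exenatide. An exenatide-only TEAE rate is therefore a coherent choice. This stands, and it is why the TEAE table should be kept. The trial also calls itself a feasibility trial, and 27 controls can show only large differences. This stands too, and it is why the added table carries no test.

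A reader might infer several stronger things that the documents do not support:

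- *That control-arm safety is not collected.* Recording runs from consent without limit by arm, and all-AE and SAE incidence is listed. The gap is grade, window and layout.
- *That the SAE percentage is undefined for SOC.* It is not; only the end of the SAE reporting period depends on dosing.
- *That SOC patients will not be asked about AEs.* This follows only if the AE section overrides *Schedule of visits*, which does not distinguish arms.
- *That the SAP assigns a mixed model to yes/no safety results.* Its sentence concerns repeated measures. Extending it to these percentages is an inference, and this point does not rely on it.

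The example in the working is also open to challenge: 22 of 54 is an arbitrary count. It shows only that one exenatide figure fits very different comparisons.

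**Conclusion.** The point holds in limited form. Followed exactly, the grade ≥2 TEAE definition leaves the randomised control out of the plan's only graded safety percentage, and no other section supplies a grade cut, window or layout that would bring it back. It is a cheap improvement to reporting. It is not a fault in the primary analysis, and it does not show that the safety objective as worded is unmet.

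The size is 27 of 81 patients without a value. The remedy is imprecise: half-widths of about 14 to 23 points, and true excesses of about 28 to 33 points needed for a reliable signal. These figures assume full enrolment at 54:27 and event rates of 10 to 50%, which the documents do not give. That SOC has no value does not depend on any assumed rate. The 81 patients and the diabetes endpoint are unaffected.

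**What to change.** 1. Keep the dose-anchored TEAE table and label it exenatide-only. Add a descriptive two-arm table of the percentage with at least one CTCAE grade ≥2 AE and the percentage with at least one SAE. Count onset, or worsening of a prior condition, from randomisation to the 24-month visit or last contact if earlier, whatever the drug status. State that CTCAE grade is assigned in both arms. Report the risk difference with 95% CI and patient-months per arm. Showing results by enrolment time is optional.
2. State that AE and SAE recording for this table runs to the 24-month visit in both arms, as the existing text on the follow-up period allows. Reconcile this with the 30-day AE follow-up after discontinuation, and with the SAE reporting period ending 90 days after the last dose, which has no end date for SOC.
3. Reconcile the AE contact timing in the AE section with *Schedule of visits*, so that within each enrolment cohort both arms are asked at the same times after randomisation.

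**Cost.** One table, short text on window and method, and CTCAE grading of AEs in 27 SOC patients. AE recording after discontinuation may also need extending if the 30-day rule is now applied as a limit. If the schedule already governs contacts, none are added for the two early calls; if the AE section does, SOC gains up to 27 × 2 = 54. The longer window includes time after early stopping and may dilute on-drug effects, which the retained TEAE table covers.

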- To compare the incidence of mesangial expansion >20% in patients treated with Exenatide SR + SOC vs. SOC alone at 24 months after kidney transplantation.
- To compare transplant kidney function in the two arms
- To compare the incidence of death by any cause in the two arms
- To compare the incidence of graft loss by any cause in the two arms.

Inclusion criteria:

- Recipients of solitary kidney transplants (i.e. not combined liver-kidney, pancreas-kidney etc.)
- Labs consistent with prediabetes, as determined at 4 and 12 months after transplantation: Prediabetes (fasting blood glucose 100-125 mg/dl; or 2 hr glucose 140-199 or HgbA1c 5.7-6.4%)

Exclusion criteria:

- Diabetes pre-transplantation
- Diabetes at 4 and 12 months
- <18 years of age
- eGFR <30 ml/min (estimated by MDRD equation from serum creatinine)
- Active acute cellular rejection including borderline (If treated and resolved, these patients can be included)
- BK nephropathy active
- History of pancreatitis, pre-existing moderate-to-severe gastroparesis, liver cirrhosis or family /personal history of multiple endocrine neoplasia 2 or medullary thyroid cancer
- Pregnant or breastfeeding women

Female Subject must be either:

- a. of non-child bearing potential
 - 1) Post-menopausal (defined as at least 1 year without any menses) prior to screening , or
 - 2) Documented surgically sterile or status post-hysterectomy
- b. Or if childbearing potential,
 - 1) Agree not to try and become pregnant during the study for at least 90 days after the final study drug administration.
 - 2) And have a negative serum or urine pregnancy test.
 - 3) And if heterosexually active, agree to consistently use two forms of highly effective birth control.

- Hypersensitivity to Exenatide

Criteria for Discontinuation of Medication:

- Decrease in renal function to eGFR to < 30 ml/min after study initiation
- Decrease in eGFR by 50% on the 2 consecutive measurements without otherwise identified cause which maybe correctable (like high immunosuppressive medication level, rejection, urinary tract infection, etc)
- Intolerable GI side effects despite the optimal therapy
- Thyroid tumor
- Pancreatitis
- Hypoglycemia

Study design/schedule

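### The adjusted diabetes comparison names no covariate and no analysis is called decisive; baseline HbA1c and enrolment cohort should be fixed as covariates in advance

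*Combined protocol and SAP*

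**What the plan says.** The Statistical analysis plan section compares the arms on time to diabetes with Kaplan-Meier curves, "utilizing log-rank tests to evaluate intergroup differences". The next sentence adds the adjusted analysis: "Risk adjustment for baseline differences between groups will be assessed according to multivariate proportional hazards models". Nothing more is said about covariates. HbA1c, fasting glucose, enrolment time point and site are not mentioned as model terms, there is no rule for what counts as a difference, and neither result is given priority.

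The sample size in the same section rests on a third method, a "2-sided chi-squared test at a 5% significance level and 80% power", with "30% incidence of PTDM in the control group and 80% risk reduction in the experimental group".

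Under Study design/schedule, patients "will be randomized 2:1 to receive either Exenatide SR or diet and exercise only with no medication", about half of them at month 4 and half at month 12. No stratification factor is stated. On HbA1c, that section says of the three biopsy times (months 4, 12 and 24): "Hemoglobin A1C will be performed at the same time points". The tables under Schedule of visits, as they read here, carry no HgbA1c mark in either enrolment column.

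**The concern.** Between randomised arms, a baseline difference is chance. A covariate improves a treatment comparison because it predicts the outcome, whether or not the arms differ on it. Tying adjustment to differences therefore uses the wrong criterion, and it leaves the model undefined until the data are in.

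Two things are at stake. First, the adjusted hazard ratio is open to choice: an analyst could defend many covariate sets under this sentence. With a prognostic covariate, the hazard ratio also changes meaning with the model even when the arms are perfectly balanced, so the choice moves the reported effect. Second, the trial expects few events, and a baseline measure closely tied to the endpoint may be left out. HbA1c serves both for eligibility and as one of the diabetes criteria, so a patient's starting value is a natural candidate predictor. Enrolment cohort is a design factor that fixes whether follow-up lasts 12 or 20 months.

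**Working it through.** **1. The plan's own figure.** Inputs from the Statistical analysis plan: control 30%; treated 0.30 × (1 − 0.80) = 6%; ratio k = 2; two-sided 5%; 80% power. The pooled rate is (0.30 + 2 × 0.06)/3 = 0.14.

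n(control) = [1.960 × √(0.14 × 0.86 × 1.5) + 0.842 × √(0.30 × 0.70 + 0.06 × 0.94/2)]² / 0.24² = [0.833 + 0.411]² / 0.0576 = 26.9, so 27 and 54. This matches "A total of 81 (54:27 according to 2:1 randomization) patients will be required", with power 80.2%. The figure assumes no covariate adjustment.

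**2. Information available.** Expected events: 27 × 0.30 + 54 × 0.06 = 8.1 + 3.24 = 11.3. Under constant hazards the implied hazard ratio is ln(0.94)/ln(0.70) = 0.17. A model with arm, HbA1c and cohort has 11.3/3 ≈ 3.8 events per parameter, so a longer list is not supportable. The chance of no event at all on exenatide is 0.94^54 ≈ 3.5%. In that case the Cox estimate is not finite, but a score test still exists.

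**3. Power with and without adjustment.** The documents give no prognostic strength for HbA1c, so the hazard ratio (HR) per standard deviation (SD) is an assumption and is varied. All runs use 27:54, 30% against 6% and exponential event times. Each cell shows log-rank → adjusted score test.

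| HR per SD | A: exact times, HbA1c only | B: exact times, HbA1c + cohort, 12/20 months | C: as B, events seen only at HbA1c marks |
|---|---|---|---|
| 1.65 (A: 1.6) | no gain | 84 → 85% | 82.9 → 82.8% |
| 2.2 | 83 → 87% | 84 → 87% | 81.8 → 84.4% |
| 2.7 | 83 → 89% | 85 → 89% | 81.0 → 84.4% |
| 3.7 | 83 → 93% | 84 → 93% | 81.3 → 86.6% |

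Replicates: A 1,500 to 6,000; B 3,000; C 2,000 (Monte Carlo error at 83% in C: √(0.83 × 0.17/2,000) = 0.8 points). C assumes detection at post-enrolment months 8, 11, 14, 17 and 20 for the month-4 cohort, and only at the end for the month-12 cohort. A further run of 1,000 replicates gave gains of 3 to 8 points with exact times and 0 to 6 points with visit detection over 2.2 to 3.7. At HR 1.0 the two tests in B were within 0.5 points (83.3% and 83.8%); the further run showed at most about a point lost.

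**4. Size of the tests.** With 14% in both arms, the one-covariate score test had size 5.0 to 5.4% and the log-rank 4.0 to 4.5%. Calibrating both to 5% gives 87, 89 and 92% against 84, 85 and 84% for column A, which are gains of 3, 4 and 8 points. The two-covariate score test ran at 5.6 to 6.3% with exact times and near 4% under visit detection.

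**5. A weaker effect.** At 30% against 12% with HR per SD of 2.7 to 3.7, power rises from 54–55% to 62–68%.

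**6. The estimate itself.** Holding incidence at 30% and 6%, the covariate-conditional treatment hazard ratio is 0.173, 0.167, 0.143 and 0.109 at HR per SD of 1.0, 1.65, 2.7 and 4.5. Adjusted and unadjusted hazard ratios are different quantities.

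**The case against.** The strongest reply is that the first-named comparison is the log-rank test, which is fixed in advance and involves no covariate choice. The Cox sentence reads as supportive. This stands in part: the freedom affects only the adjusted result, unless that result is treated as decisive, and the text leaves that open.

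Four stronger readings are tempting and should not be drawn.

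- *The trial is underpowered without adjustment.* It is not, on its own assumptions: the log-rank test has roughly 80 to 85% power at 30% against 6% in these runs.
- *The plan screens covariates by an imbalance test.* It states no trigger. If one assumes a p<0.05 trigger, a given covariate enters in about 5% of trials and almost none of the gain is recovered, but that trigger is an assumption.
- *The wording inflates type I error.* Selecting by imbalance from eight covariates gave 5.2 to 5.4%. Inflation to 6.6–8.6% (HR per SD 1.65 to 4.5, 30% in both arms) appeared only when the better of the adjusted and unadjusted results was reported. The plan does not propose that, though it does not exclude it.
- *HbA1c is the dominant predictor and is assured at baseline.* Eligibility reads "Prediabetes (fasting blood glucose 100-125 mg/dl; or 2 hr glucose 140-199 or HgbA1c 5.7-6.4" per cent, so a patient can qualify on glucose alone with HbA1c outside that range. HbA1c is one of four alternative diabetes criteria, and fasting glucose has a comparable textual claim as a covariate. The visit tables do not confirm an enrolment HbA1c.

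**Conclusion.** The point holds as one of pre-specification, with a modest and conditional gain in power. The adjusted model cannot be determined from the plan before the data are seen, no analysis is named as decisive, and a likely predictor may go unused.

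Against the log-rank test, always adjusting is worth about 0 points if HbA1c has a hazard ratio per SD of 1.65 or less. At 2.2 to 3.7 it is worth about 3 to 10 points with exact event times, and about 0 to 6 points if diabetes is found only at scheduled HbA1c visits. These ranges rest on an assumed prognostic strength, complete baseline values and exponential event times. The case for naming the model in advance does not depend on them.

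**What to change.** Replace the risk-adjustment sentence with a statement that:

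- the treatment comparison is adjusted in every case for baseline HbA1c (continuous) and enrolment cohort (month 4 or month 12), using the score test from the proportional hazards model, optionally with a permutation reference distribution because so few events are expected;
- no covariate is added or dropped because of observed imbalance;
- one analysis is named as decisive;
- the unadjusted log-rank test is reported alongside, and the hazard ratio is labelled as conditional on the two covariates.

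The text change is short and needs no extra patients. It has two costs. The HbA1c timing under Study design/schedule and the Schedule of visits tables must be reconciled, so that it is clear whether every patient has an enrolment value. A simple rule for a missing baseline HbA1c must also be written before the data are seen, for example the mean of observed baseline values pooled over both arms. If HbA1c proves uninformative, the power lost is about a point at most.
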